### ***Selection of Subjects***

The study population will consist of up to 30 subjects recruited from the associated UCLA outpatient clinics. The selection of suitable subjects will be made according to the inclusion and exclusion criteria described below.

#### ***Inclusion Criteria***

Male and female adults (18 to 70 years) with plantar heel pain and point tenderness near the medial calcaneal insertion of the plantar fascia for at least three months without improvement will be considered for inclusion into the study.

Subjects must be willing and able to follow post treatment regimen including immobilization boot for 2 - 4 weeks after each treatment, and massage therapy.

#### ***Exclusion Criteria***

Subjects with diabetes or other circulatory issues that might impede healing, bilateral plantar heel pain, current systemic or local infection (within the last 30 days), previous foot surgeries, other previously diagnosed foot/ankle pathologies (inflammatory arthritis, gout, neurologic disorders, connective tissue disorders, bone spurs and fragments and malignancy), unwilling or unable to complete post regimen, and pregnancy will be excluded. Also excluded are subjects with thick calluses on their heel, making ultrasound imaging and treatment of the plantar fascia difficult.

### ***Interventions***

Standard of care treatment will include massage 5 minutes daily as defined by PI and the use of an immobilization boot along with an orthotic insert for 2 to 4 weeks after the each treatment. The decision to continue or discontinue the boot will be made during the follow-up phone call 2 weeks after each treatment. The caller will discuss (Appendix 1-F) the subject's progress and come to a decision on continuing or stopping the use of the boot. When it is determined that a subject can stop using the boot, they will continue to use the orthotic insert in firm soled shoe that does not flex or bend – Tennis shoe, platform, wedge, Birkenstock or FitFlop™ sandal. At that point the subject can resume light activities: Walking on a flat, hard surface (no hiking trails), bicycling and light exercises. Subject will massage region twice a day for 2 ½ minutes per each time, total 5 minutes/day.

During Visit 2 (4 weeks after the first treatment), subjects will receive a second treatment if heel pain is not 90% resolved. The use of the boot and orthotic will resume as defined after the first treatment. If a week 4 visit is not possible we will allow a 2nd treatment at week 6, if such treatment is deemed necessary. If a 2nd treatment is moved to week 6, subsequent follow-up dates will be adjusted accordingly. ITU treatments will be performed using a GEN III system (Guided Therapy Systems, Mesa, AZ, Appendix 4). Trained study personnel will conduct the treatments. The treatment session will last 15 – 20 minutes. During this time the subjects will be required to lay prone on an exam table with their feet hanging over the end of the table. An average energy up to 5 joules / thermal zone will be administered to the plantar fascia in a linear pattern (Figure 1) with up to 360 thermal zones. Each thermal zone will be less than 1 mm^3 in volume, centred at 10 - 15 mm depth, and approximately 1-3 mm apart.

[figure not shown]

Figure 1: The treatment site located around the insertion of the plantar fascia onto the posterior process of the calcaneus

#### Treatment pattern transverse across the Plantar Fascia:

[figure not shown]

Figure 2. Treatment Zones

#### Outcome measures

Subjects will complete subject reported outcome instruments, and will undergo a focused physical examination and diagnostic ultrasound at 0, 4, 8, 12 weeks. At 2, and 24 weeks a phone survey will be administered by the Clinical Coordinator using the same subject report outcome questionnaires. Adverse events, if any, and treatment tolerability will be recorded at each visit and 2-3 days after each treatment.

#### Aim 1: Subject reported outcomes and structured physical exam

The principal aim of this study is to demonstrate the efficacy of treatment and time course of response to treatment and post treatment regimens using validated subject reported outcome measures assessing pain, function and level of activity and structured physical examination. Subjects will complete validated subject reported outcome questionnaires assessing pain, function and level of activity prior to initiating treatment and at 4, 8, 12, and 24 ( 24 week surveys will be completed by a phone interview) weeks after starting treatment. Subjects will also be contacted 2-3 days following each treatment to assess treatment tolerability and to document and address adverse effects (if any). They will also be contacted by phone 2 weeks after

treatment(s) to assess progress and determine if the boot can be discontinued.

**Pain** will be assessed using the of the foot function index pain subscale (FFI-P) and the subject reported outcome measures (SROM). These two instruments have been used to assess pain in previous studies of plantar fascia treatments. [22, 23]

**Function** will be assessed using two validated PRO instruments the PROMIS PF CAT and the FAAM. The PROMIS PFCAT is a subject relevant outcome measure that uses computer adaptive survey questions to assess the subject's pain and function in relation to daily activities [24]. The FAAM has been shown to be a reliable, responsive, and valid measure of physical function for individuals with a broad range of musculoskeletal disorders of the lower leg, foot, and ankle [25].

**Level of Activity** will be assessed using the activity subscale of FAAM. This subscale scores quantitatively the level of difficulty subjects face when they perform basic activities of daily living. It has shown to be an accurate and reliable predictor of the activity level while performing day-to-day activities [25]

**Structured physical examination** will consist of assessment of hindfoot and midfoot alignment, inspection for swelling, palpation of the calcaneus and entire plantar fascia, range of motion of the ankle with the knee flexed and with the knee extended, and calcaneal squeeze test. Pertinent positive findings on exam include: valgus hindfoot, midfoot planus, tenderness to palpation at the insertion of the plantar fascia onto the calcaneus, ankle dorsiflexion less than 10 degrees with the knee extended or greater than 10 degree augmentation in ankle dorsiflexion with the knee flexed. Pertinent negative findings include: lack of swelling at the ankle and midfoot, no tenderness at the Achilles insertion, the retrocalcaneal bursae, along the arch, posterior to the medial malleolus, or at Baxters point, and positive calcaneal squeeze test.

#### Statistical analysis

Data will be assessed for variance homogeneity and normality. FFI-P scores, PFCAT, FAAM scores before and after intervention will be compared using a paired t-test. Perifascial lesion volume is measured before and at each post treatment clinical visit using diagnostic ultrasound imaging, and paired t-tests will be utilized for comparison. For determination of statistical significance, a cutoff value of  $\alpha=0.05$  has been selected prior to start of data analysis.

#### Aim 2: Assessment of Perifascial Hypoechoic Lesions

Diagnostic ultrasound imaging will be performed with an FDA 510(k) cleared ultrasound scanner (Spark® System, Ardent Sound, Inc. – Mesa, AZ, see Appendix 5) using a coupling gel (Polysonic® Parker Laboratories, Inc., Fairfield, NJ, see Appendix 6) by a trained sonographer or physician. The subject will positioned prone on an exam table with the feet over the edge of the table. The plantar fascia of the affected and contralateral feet will be imaged. The thickness and depth of the fascia as well as the size and location of any hypoechoic lesion(s), when present, will be recorded using both long and short axis imaging. Change in the volume of hypoechoic plantar fascial lesions relative to the baseline measurement will be calculated.

[figure not shown]
[figure not shown]

Figure 4: representative long and short axis ultrasound images

### **Aim 3: Assessment of safety and tolerability**

Subject self-assessments of treatment tolerability will be conducted immediately after, two –three days after (phone survey) and two weeks after (phone survey) treatment using a10-point visual analog scale (VAS, see Appendix 1). The subject will be asked to report their current level of pain and the maximum level of pain experienced over the last few days. The VAS is the standard for assessing pain for both clinical and research purposes [26]. All phone surveys will be completed by the Clinical Coordinator. Any adverse effects will be noted and addressed during these phone calls.

Recording of adverse events will take place at all clinic visits and follow-up phone calls (see adverse event reporting form Appendix 3). Adverse events and serious adverse events will be monitored throughout the study.

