## Appendix 1-D: Foot function index pain subscale (0 – 10)

How severe is your heel pain?

---

1. At its worst?	No pain	Worst pain imaginable
------------------	---------	-----------------------

---

2. After you get up in the morning with the first few steps?	No pain	Worst pain imaginable
--	---------	-----------------------

---

3. At the end of the day?	No pain	Worst pain imaginable
---------------------------	---------	-----------------------

---

4. When you walk barefoot?	No pain	Worst pain imaginable
----------------------------	---------	-----------------------

---

5. When you stand barefoot?	No pain	Worst pain imaginable
-----------------------------	---------	-----------------------

---

6. When you walk wearing shoes?	No pain	Worst pain imaginable
---------------------------------	---------	-----------------------

---

7. When you stand wearing shoes?	No pain	Worst pain imaginable
----------------------------------	---------	-----------------------

---

8. When walking with orthotics?	No pain	Worst pain imaginable
---------------------------------	---------	-----------------------

---

9. When standing with orthotics?	No pain	Worst pain imaginable
----------------------------------	---------	-----------------------

---

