## Appendix 1-F: Boot Continuance Decision Checklist

2 Weeks after Treatment:      1      2  
Circle Appropriate Time

Ask the Subject about their overall pain from a Scale of 0 – 10.  
Mark the Universal Pain Assessment Tool below.

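### Asked immediately after ITU, the maximum-pain tolerability question covers mostly pre-treatment days and cannot separate procedure pain from existing heel pain

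*Protocol*

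**What the plan says.** Protocol, Aim 3, sets three contacts per treatment: "Subject self-assessments of treatment tolerability will be conducted immediately after, two –three days after (phone survey) and two weeks after (phone survey) treatment". The scale is a 10-point VAS, and one wording serves all three: "The subject will be asked to report their current level of pain and the maximum level of pain experienced over the last few days". Nothing gives the immediate or two-week contact its own window, ties the maximum to the session, or asks subjects to leave out earlier heel pain. The pain scale in Appendix 1-C has no recall period.

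Heel pain is present before each treatment by design. Inclusion requires "plantar heel pain and point tenderness near the medial calcaneal insertion of the plantar fascia for at least three months without improvement". At Visit 2, according to Interventions, "subjects will receive a second treatment if heel pain is not 90% resolved".

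The Protocol is not consistent about the two-week contact. Outcome measures says that "treatment tolerability will be recorded at each visit and 2-3 days after each treatment" and does not name two weeks for tolerability. The tolerability row of the Timeline marks only the calls at 2–3 days. The two-week form (Appendix 1-F) has a single item, "Ask the Subject about their overall pain from a Scale of 0 – 10", with no maximum and no window.

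Neither the Protocol's Statistical analysis section nor the SAP describes an analysis of the tolerability scores.

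**The concern.** Tolerability and safety form the secondary objective. For a thermal procedure, the pain felt while it is delivered is a natural measure of tolerability. The recall window suits the call at 2–3 days reasonably well, but not the contact straight after the session. There the maximum item asks mainly about the days before treatment, and the current-pain item is asked once the session is over. Neither gives the pain of the session itself.

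The efficacy pain scores are also self-reported on 0–10 scales and concern the same heel (Appendix 1-D asks "How severe is your heel pain"). A high maximum immediately after ITU could therefore reflect a painful session or an ordinary bad day earlier that week. The same window at two weeks would leave a stretch after the first few days with no maximum score.

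**Working it through.** The plan states no tolerability figure, so there is nothing to reproduce. Three checks follow.

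**1. Immediate contact.** The session lasts 15–20 minutes (Interventions). *Few* is not defined; I take w = 2 to 4 days and extend to 5. The largest share of the window that the session can fill is 20 / (2 × 24 × 60) = 20 / 2,880 = 0.7%. At least 99% of the window is before treatment. The item records max(pre-treatment worst heel pain, procedure pain). For example, with assumed scores, worst heel pain of 7 and procedure pain of 3 give a recorded 7.

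**2. How much the item compresses real differences.** The documents do not give pre-treatment worst pain or procedure pain, so all inputs here are assumptions. Both scores are normal with SD 2, rounded and bounded at 0–10, with correlation 0 or 0.5, and every subject answers literally. Mean procedure pain is set at 3, 5 or 7, and the mean of pre-treatment worst pain is varied. The reported difference is mean of max(pre, procedure) at 7 minus the same mean at 3.

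| Assumed mean pre-treatment worst pain | Reported difference when the true difference is 4 | Share whose pre-treatment pain exceeds procedure pain, procedure mean 5 |
|---|---|---|
| 6.5 | 1.0–1.2 | 64–69% |
| 5 | 1.9–2.0 | 40–43% |
| 4 | 2.5–2.6 | 23–30% |
| 3 | 2.9–3.2 | 11–19% |

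For example, at 6.5 with zero correlation the reported means are 6.62 and 7.81, a difference of 1.19. I reran the model and these figures reproduce. Bounding and rounding alone would take the 4 points only to about 3.9, so almost all of the loss comes from the recall window.

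**3. Coverage of days 0–14, if the two-week question is asked.** With the first call on day c = 2 or 3:

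- Days missed by the two-week item alone = 14 − w.
- Days after treatment covered by no maximum item = (14 − w − c) + max(0, c − w).
- Share of the first call's window that falls before treatment = max(0, w − c) / w.

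| w (days) | Missed by two-week item alone | Joint gap | Pre-treatment share of the 2–3 day call |
|---|---|---|---|
| 2 | 12 | 10 (71%) | 0% |
| 3 | 11 | 8–9 (57–64%) | 0–33% |
| 4 | 10 | 7–8 (50–57%) | 25–50% |
| 5 | 9 | 6–7 (43–50%) | 40–60% |

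For example, w = 3 and c = 3 gives (14 − 3 − 3) + 0 = 8 days. With windows tied to events, the pre-treatment share at the immediate contact and the joint gap both become zero.

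**The case against.** The strongest reply is that the documents already hold much of what is needed. The Timeline schedules the pain survey at Visits 1 and 2, the treatment visits. The SAP uses a pre-treatment pain score as baseline, and the first item of the foot function index asks for heel pain at its worst. An immediate maximum above that score would show up as procedure pain. This stands in part: the item fails only where procedure pain stays below recent worst heel pain. But the documents do not link the two scores, and the Timeline does not say that the Visit 2 survey precedes ITU.

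A reader might infer that a flare between the calls would be lost. The documents do not support that. Adverse events are recorded at all visits and follow-up calls, and the form in Appendix 3 has start and end dates, severity and relation to ITU. What is lost is a 0–10 score, not necessarily the event.

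A reader might also take this VAS to be the only patient-reported response to treatment. It is not: Appendix 1-E asks about satisfaction with the treatment and about being worse or having more pain. Those items do not score procedure pain, however.

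Finally, the two-week question rests on Aim 3 alone. Outcome measures does mention a week-2 phone survey using the outcome questionnaires, whose worst-pain item has no recall period, but Aim 1 and the Timeline do not schedule the survey then. The two-week gap is therefore conditional.

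**Conclusion.** The point holds for the maximum item at the immediate contact, and it follows from the wording for any window longer than the session. The item cannot separate procedure pain from existing heel pain, and nothing else measures pain during ITU.

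The size is uncertain. It is tempting to conclude that a 4-point difference always shrinks to about 1 point, or that well and poorly tolerated sessions look alike. That needs high pre-treatment pain, which the documents do not establish. The SAP allows for baseline scores of 2–5, and subjects who have partly improved can still receive treatment 2. Over assumed means of 6.5 down to 3, the reported difference runs from about 1.0 to 3.2 points.

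At two weeks, if the question is asked there, the gap is about 7–10 of 14 days for a 2–4 day window and 6–7 days for a 5-day window. To say that the scheme misses most of recovery would go too far: that describes the two-week item alone, and the documents do not define a recovery period.

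The effect is confined to the Aim 3 tolerability scores. Efficacy comparisons, sample size and alpha are untouched. It is worth correcting because the correction is cheap and makes part of the secondary objective answerable.

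**What to change.** In Aim 3, give each contact a maximum tied to an event:

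- Immediately after ITU: maximum pain during the session, plus current pain.
- At 2–3 days: maximum pain since the session, plus current pain.
- At two weeks, if retained: maximum pain since the previous call, plus current pain.

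State that the pain score already scheduled at the treatment visits is taken before ITU, and use it as the same-day reference. Report the during-session maximum and the change from that reference, separately for treatments 1 and 2.

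Reconcile Aim 3 with Outcome measures, the Timeline and Appendix 1-F on whether tolerability is assessed at two weeks. If it is, add the item to that form.

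The cost is a few reworded questions at contacts that already take place and, if the two-week assessment stays, one more item on that form. Scores would be less directly comparable with the earlier ITU study described in the Protocol's background, if that study used the present question.

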**Timeline**

Procedures	Visit 0	Visit 1	Visit 1 Follow-up Phone Interview Treatment Tolerability	Treatment 1 Follow-up Phone Call: Boot Decision	Visit 2	Visit 2 Follow-up Phone Interview Treatment Tolerability	Treatment 2 Follow-up Phone Call: Boot Decision	Visit 3	Visit 4	Phone Interview Subject's Progress Survey 2	Responsibility
	Baseline -14 - 0 Days	Week 0	Week 0 (+ 2 or 3 days)	Week 2	Week 4	Week 4 (+ 2 or 3 days)	Week 6	Week 8	Week 12	Week 24	
IC, eligibility paperwork, exam for inclusion criteria	X										PI/Clinical Coordinator (CC)
Ultrasound Imaging		X			X			X	X		GTS or PI
ITU Treatment		X			X (If required)						GTS or PI
TBD Clinical grading for Plantar Fasciitis severity	X	X			X			X	X		PI (cc documentation)
Subject Survey – Pain Scale and Ankle Mobility Scale		X			X			X	X	X Phone Interview	Subject (cc documentation)
Boot and Instructions		X		X			X If 2nd Treatment is Performed				PI (cc documentation)
Shoe, Insert and Instructions		X		X			X If 2nd Treatment is Performed				PI/CC
Follow-up call Treatment Tolerability			X			X If 2nd Treatment is Performed					PI/CC
Telephone Interview & Determine if Boot is continued (Week 2 and 6 only)				X			X If 2nd Treatment is Performed				PI/CC

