### ***Purpose of Study***

The purpose of this study is to assess the effectiveness of ITU in the treatment of CPF by assessing pain, function, and change in perifascial lesions treated with ITU in addition to standard of care. The primary outcome measures will be clinical grading for plantar fasciitis/osis grading and subject reported questionnaires where pain, function and level of activity will be compared before, during and at 24 weeks after the first of 2 treatments. In addition diagnostic ultrasound images will assess the change of any perifascial hypoechoic lesions. Finally, the safety and tolerability of ITU will be monitored through the course of the study. It is hypothesized that patients receiving ITU in addition to standard of care will have a more rapid resolution of their pain, faster return to activities, and a decrease in perifascial lesions.

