TITLE: Preliminary Protocol for Intense Therapeutic Ultrasound for the Treatment of Chronic Plantar Fasciitis

PROTOCOL NO.: WIRB® Protocol #20160753

DATE: May 26, 2016

SPONSOR: Guided Therapy Systems

[name]

[name]

INVESTIGATOR: [name]

[name]

[name]

Statistical Approach:

- Pain Reduction:

Pain level at the plantar fascia was self-reported by subjects at pre-treatment (used as baseline measurement) and again at each follow-up - 4, 8, 12, and 26 weeks - after initial treatment. The pain scale subjects used to identify their level of pain was a 10-point pain scale range, where 0 = no pain, 1 = slight pain through 10 which equates to the patient's worst imaginable pain. The goal for all subjects in the treatment group was to reduce pain by at least 25%. For patients reporting an initial (baseline) score ranging 6-10, this reflects a VAS pain score reduction  $\geq$  a 2 point drop; for initial scores ranging 2-5, this reflects a VAS pain score reduction  $\geq$  a 1 point drop. Pain scores reported at follow-up timepoints were compared to baseline score for each subject to determine if the goal was met by dividing the difference in the follow-up and baseline pain score by the baseline pain score. The percentage of subjects that met the pain reduction goal was calculated at each timepoint for both control and treatment groups by dividing the number of subjects that achieved the pain reduction goal at each timepoint by the total number of patients that gave a pain score for that time point.

- Plantar Fascia Hypoechoic Lesion Size:

A large proportion of patients suffering from chronic plantar fasciitis present with hypoechoic lesions in or around the proximal plantar fascia, as viewed by diagnostic ultrasound imaging.

Hypoechoic lesions were imaged and volumes were calculated at the baseline visit and each follow-up visit by measuring the inferior-to-superior and posterior-to-anterior radii in the long axis and the medial-to-lateral radius of the transverse axis and applying the following formula for the volume of an ellipse:

$$\text{Volume} = (4/3)\pi \cdot r_1 \cdot r_2 \cdot r_3$$

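### With no defined control group and a single pre-treatment pain and function score, fluctuation and continuing trend cannot be told apart from treatment response, and Visit 0 is not used to gauge them

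*Protocol*

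**What the plan says.** The Timeline gives Visit 0 the window "Baseline -14 - 0 Days". Consent, eligibility and the row "TBD Clinical grading for Plantar Fasciitis severity" are marked there. The row "Subject Survey – Pain Scale and Ankle Mobility Scale" is first marked at Visit 1 (Week 0), when ITU, boot and insert also start.

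The other sections agree on one pre-treatment score. Protocol, Outcome measures: "Subjects will complete subject reported outcome instruments, and will undergo a focused physical examination and diagnostic ultrasound at 0, 4, 8, 12 weeks". Protocol, Aim 1, places the questionnaires "prior to initiating treatment and at 4, 8, 12, and 24" weeks. SAP, Pain Reduction: "Pain level at the plantar fascia was self-reported by subjects at pre-treatment (used as baseline measurement", and each follow-up score is compared with it. Both documents test follow-up against baseline with t-tests at alpha 0.05.

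The SAP's responder goal is a fall of at least 25%. It is also expressed as at least 2 points for baselines of 6-10 and at least 1 point for baselines of 2-5. The SAP says the percentage meeting the goal is calculated for control and treatment groups. The protocol describes no control arm or allocation, and the SAP plans no between-group test.

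Two features give partial protection. Eligibility requires heel pain "for at least three months without improvement will be considered for inclusion into the study", and clinical grading is taken at both Visit 0 and Visit 1. Protocol, Purpose of Study, counts that grading among the main outcomes: "The primary outcome measures will be clinical grading for plantar fasciitis/osis grading and subject reported questionnaires".

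**The concern.** The primary objective is efficacy, and the evidence is change from one score in subjects who all receive ITU together with massage, boot and orthotic. The protocol's Background says conservative care succeeds in 90% of patients within 12 months, so improvement without any ITU effect is plausible.

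Two distinct things can look like response:

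- **Fluctuation.** If nothing selects subjects on their Visit 1 score, chance highs and lows cancel in the mean change. They do not cancel in a responder count, where chance falls are counted and chance rises are not subtracted.
- **Trend after Visit 1.** This shifts both the mean change and the responder rate.

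The interval from Visit 0 to Visit 1 is the only scheduled time before treatment. Because no pain or function score is taken at its start, the trial yields no figure of its own for change without treatment.

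**Working it through.** The documents give no SD, correlation, effect size or power figure, so there is no stated result to reproduce. From the documents: n up to 30, alpha 0.05, a Visit 0 window of 0 to 14 days, and the 2-point and 1-point rules. **Assumed:** 0-10 scale, SD 2, normal continuous scores, between-visit correlation r from 0.5 to 0.9, two-sided tests.

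**1. Responders by fluctuation alone.** With no true change, the SD of a difference is 2 × √(2(1 − r)), and P(fall ≥ k) = Φ(−k / SD of difference), averaged over all baselines.

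| r | SD of difference | P(fall ≥ 2) | P(fall ≥ 1) |
|---|---|---|---|
| 0.9 | 0.89 | 1% | 13% |
| 0.8 | 1.26 | 6% | 22% |
| 0.7 | 1.55 | 10% | 26% |
| 0.5 | 2.00 | 16% | 31% |

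The SAP applies the 2-point rule to the higher baselines, where a chance fall is likelier than average. For one subject 2 points above the mean at Visit 1, the expected fall is (1 − r) × 2 and the residual SD is 2√(1 − r²). At r = 0.7 these are 0.6 and 1.43, so P(fall ≥ 2) = Φ(−1.4/1.43) = 16%. That figure describes one such subject, not the cohort.

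**2. Continuing trend and the paired t-test.** Suppose ITU has no effect and the mean background improvement is d. The noncentrality is d / (SD of difference/√30). For d = 0.5 / 1.0 / 1.5 points, the test gives p < 0.05 with probability 26% / 75% / 98% at r = 0.5, and 40% / 93% / over 99% at r = 0.7. The nominal rate is 5%.

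**3. Where regression from selection falls.** Suppose entry in effect requires Visit 0 pain of at least 5 in a population with mean 5 and SD 2 (an assumption, since the protocol sets no threshold). The mean excess at Visit 0 is 2 × 0.798 = 1.60 points. Regression is (1 − reliability) × 1.60 = 0.80 / 0.48 / 0.16 points at reliability 0.5 / 0.7 / 0.9.

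- With separate days and independent visit errors, all of it occurs before Visit 1 and none enters the change from Visit 1.
- With a 14-day gap and errors decaying with a half-life of 1 to 8 weeks, 0.04 to 0.49 points fall between Visit 1 and week 12.
- If both visits are on one day, 0.10 to 0.80 points fall after baseline by week 12.
- Averaging Visit 0 into the baseline would put half of the regression (0.40 / 0.24 / 0.08) into the measured change in the independent-error case.

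**4. What a Visit 0 score would give.** With 30 subjects all seen on different days, the SE of the Visit 0 to Visit 1 change is 2√(2(1 − r))/√30 = 0.37 / 0.28 / 0.16 at r = 0.5 / 0.7 / 0.9. Multiplying by 1.96 gives 95% half-widths of about 0.7 / 0.6 / 0.3 points. Extrapolating linearly from 14 days to 12 weeks multiplies these by 6 (4.3 / 3.3 / 1.9 points). To 24 weeks the factor is 12 (8.6 / 6.7 / 3.8). On a 0-10 scale those extrapolations are uninformative.

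**The case against.** The strongest reply is that the missing survey is not the cause. The confounding comes from an uncontrolled before-after comparison with co-interventions, and a Visit 0 score cures neither. That stands.

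A reader might also infer that improvement already made before treatment is credited to ITU. The documents do not support this: baseline is the Visit 1 score, so gains completed by then are excluded. At an assumed trend of 0.05 points a week, the 0.1 points gained in the 14 days before Visit 1 are not counted, while 0.6 points by week 12 are.

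Nor do they support the inference that regression from selection at Visit 0 passes wholesale into the result. Taking baseline after screening removes much of it, as step 3 shows. The exposure is greatest when the visits coincide, and there a Visit 0 survey adds nothing.

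The existing safeguards deserve credit but are limited. The no-improvement criterion rests on history, not a score. The repeated grading has a scale still to be determined, and no comparison of the two grades is planned. FFI-P asks separately about first steps and end of day, which handles part of the within-day variation but not variation between days.

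**Conclusion.** The point holds as a limit on what the trial can show. With one pre-treatment score and no defined control, neither fluctuation nor a continuing trend can be separated from response, and the number of subjects meeting the SAP's goal by fluctuation cannot be estimated. Under SD 2 and r = 0.7 that number is about 10% for a 2-point and 26% for a 1-point fall; across r from 0.9 to 0.5 the ranges are 1-16% and 13-31%. All of these rest on assumed values and a normal, continuous approximation to a whole-number scale.

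A Visit 0 survey is a worthwhile secondary measure. It would describe short-term stability to within about 0.6 points at r = 0.7, if all 30 subjects have separate visits. It would not isolate the effect of ITU.

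**What to change.** 1. In the Timeline, mark the Subject Survey at Visit 0 as well as Visit 1, naming the instruments: 0-10 pain, FFI-P and FAAM.
2. Keep Visit 1 as the analysis baseline. Use the mean of the two visits only in a sensitivity analysis.
3. For subjects whose two visits fall on different days, report the Visit 0 to Visit 1 change with its 95% confidence interval, and the proportion meeting the SAP's responder rule over that interval. Put both beside the week 4 results, give the number of subjects and the gap in days, and do not extrapolate to week 12 or 24.
4. State which responder rule applies. The point drops fall short of 25% at baselines of 5 (1/5 = 20%), 9 (2/9 = 22%) and 10 (2/10 = 20%).
5. Describe results as change from baseline on ITU plus standard care, not as efficacy of ITU. Either define the control group named in the SAP and plan a between-group comparison, or remove the reference to it.

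The cost is a few minutes of questionnaires at a visit already held, and a short SAP addition. The interval is short and variable, FAAM's one-week recall periods overlap when the gap is under 7 days, and same-day subjects contribute nothing. The SAP is written in the past tense. If data collection is complete, items 1 to 3 are no longer possible, and the remaining action is to state the limitation and apply items 4 and 5.
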